3 OBJECTIVES

3.1 Study Objectives

Primary: The primary objective is to quantify the difference in proportion of SOCLs treated operatively when a diagnostic device is used compared to when one is not used and to quantify the difference in proportion of SOCLs treated surgically that extend into dentin when a diagnostic device is used compared to when one is not used.

Secondary: The secondary objectives are to identify the clinical characteristics of SOCLs that best predict caries that extends into dentin, to determine whether the principal factors used by participating practitioners in managing SOCLs change when a caries detection device is employed, and to obtain practitioners' assessments of the utility of the devices in their practices. Because the vignettes are designed to simulate the clinical situations for which data collection will occur, their fidelity in predicting practitioners' treatment decisions will also be assessed, providing a unique and needed insight into their utility for future studies of diagnostic decision-making.

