- 4. Device Familiarization: Practitioners randomized to the device arm will familiarize themselves on device use, thus simulating as closely as possible what occurs in practice if dentists purchase devices on their own. Practitioners will "self-train" according to manufacturer's instructions and manufacturer-provided materials (e.g. DVD, Webinar). Practitioners may seek further guidance on device use from their colleagues and may query a manufacturer representative. Device Familiarization will also involve practitioners familiarizing themselves with the devices through unsupervised clinical use with patients. This device familiarization period is anticipated to take approximately four weeks for all practitioners randomized into the device arms.

Before beginning the clinical portion of the study, practitioners will complete pre-study vignettes that require practitioners to make diagnostic decisions with scenarios and photos. They will be asked how likely they would be to choose a specific treatment procedure. This vignette will be completed online. Following the vignette, all practitioners will participate in an approximate 4 week long pre-intervention period without the assistance of a caries detecting device and will enroll patients with at least one lesion. Practitioners will record data for one lesion per patient, which will be determined randomly. If more than one lesion is found in one patient, practitioners will choose the tooth that is closest to the day of the month on the day they are observing the patient. They will choose the tooth in an ascending order. For example, if the day of the month is the fourth, the practitioner will choose the higher number tooth closest to the fourth. Data to be recorded include pre-treatment

findings, a treatment decision, and if necessary, post-treatment findings. If, during the first two weeks of the pre-intervention period, practitioners are unable to enroll five patients with a SOCL, or do not wish to further participate in the study, they may be withdrawn and new practitioner(s) will take their place prior to randomization. The goal for enrollment is approximately 20 enrolled/completed patients each with one SOCL.

Following the pre-intervention period, practitioners will be randomized into one of three arms (Spectra[®], DIAGNOdent[®], and no device). Practitioner randomization will occur after the pre-intervention period.

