7 STUDY PROCEDURES/EVALUATIONS

7.1 Study Procedures/Evaluations

Practitioner: The practitioner will complete a pre-study vignette online. After the study is complete, he/she will also complete a post-study vignette and questionnaire. For the pre-and post-study vignettes, practitioners will be given scenarios with photos. They will be asked to indicate how likely they would be to recommend a variety of treatments based on four cues: color, luster, and roughness of the lesion and caries risk characterization.

Patient: Once a patient has consented to participate and is enrolled, assessments are performed for the study based upon clinical examination findings and recorded on data collection forms. The forms will require the following information:

Provided by patient

• Subject age, sex, race, and ethnicity

Provided by practitioner

- Subject caries risk information;
- Clinical description of the lesion;
- Description of treatment provided;
- Clinical description of opened lesion, if operative intervention undertaken; and
- Practitioner's assessment of patients' caries risk category

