To determine whether the principal factors used by participating practitioners in managing SOCLs change when a caries detection device is employed, the Lens model analytic approach will allow for the determination of the unique contribution of each of the 4 principal features (color, luster, roughness, risk) to the treatment decision. An overall significance of each equation and the variance it accounted for will be determined for the decision to surgically intervene and the confidence of that decision. These represent the main a priori hypotheses from the decision study (vignette) portion of the project. In addition to those a priori hypothesized analyses, a number of more exploratory analyses are possible within the Lens model approach. This could include demographic characteristics of the dentists (age race, sex, experience in practice etc.). These individual difference variables would be included in the nomothetic analyses only. Finally, the similarity of treatment predictors will be examined across the in vivo and vignette portions of the study as an initial cross validation of the two approaches. We will examine the concordance rates and/or correlations between number of decisions to intervene across the two portions of the study and across groups (device trained vs. no device).

The proposed sample size, developed in the previous section was developed using conservative assumptions regarding effect size and potentially missing data. The study is anticipated to provide adequate statistical power even if approximately 20% of observations have missing values for some variables, depending on the differences and level of ICC that are actually observed in the study. Issues regarding missing values are presented in further detail in the Appendix E.

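### The count-based part of the vignette fidelity check cannot separate fidelity from case mix and small-count noise, and the vignette response described does not match the outcomes to be analysed

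*Protocol*

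**What the plan says.** Section 3.1 lists, with the secondary objectives, an assessment of the vignettes: "their fidelity in predicting practitioners' treatment decisions will also be assessed". Section 11.3 plans two checks. The first asks whether the same predictors drive treatment in the clinic and in the vignettes, and is labelled an initial cross-validation. The second is: "We will examine the concordance rates and/or correlations between number of decisions to intervene across the two portions of the study", also broken down by device-trained against no-device practitioners.

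The two sets of lesions differ in origin. Section 7.2 gives 16 profiles, each with a text vignette and a photograph, varying in color, luster, roughness and caries risk. Section 4 gives about 20 lesions per practitioner in each phase, drawn from that practitioner's own patients.

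On the response collected, Section 4 says: "They will be asked how likely they would be to choose a specific treatment procedure". Section 7.1 says: "They will be asked to indicate how likely they would be to recommend a variety of treatments based on four cues". Section 4 also says that "practitioners will complete pre-study vignettes that require practitioners to make diagnostic decisions with scenarios and photos". Section 11.3 then names the outcomes of the Lens equations: overall significance and variance accounted for "will be determined for the decision to surgically intervene and the confidence of that decision". It adds: "These represent the main a priori hypotheses from the decision study (vignette) portion of the project".

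**The concern.** The objective concerns prediction: does what a dentist says on a vignette tell us what that dentist does with a patient? A count of interventions depends on the dentist's rule, on the lesions to which it is applied, and on chance. The vignette lesions are the same for everyone; the clinical lesions are not. Section 5.1 admits general and pediatric dentists and patients from age six, and selects teeth on roughness, opacities or staining, which overlap with the vignette cues. The clinical mix may therefore differ from the vignette mix and between practices. Because no clinical lesion corresponds to a profile, a lesion-level concordance rate is not defined. Only totals or rates per practitioner can be compared.

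A low correlation, or a gap between the two rates, would then be hard to interpret on a stated secondary objective.

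The response wording is a separate matter. The protocol describes a graded likelihood for each treatment. The count needs a yes/no decision, and the second Lens outcome needs a confidence rating. No item giving confidence is described.

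**Working it through.** The protocol states no sample size, power or expected value for the fidelity analysis, so there is no figure of its own to reproduce. The results below show what the count comparison would give if fidelity were perfect.

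**1. Ceiling from small counts, identical case mix.**
- Inputs: 16 profiles (Section 7.2); 20 lesions in a phase (Section 4); ICC from 0 to 0.05 (Section 11.2). Section 11.2 applies the ICC to clinical lesions; using it for the vignettes as well is an assumption.
- The share of a count's variance that reflects the practitioner is rel(m) = m × ICC / (1 + (m − 1) × ICC).
- If the practitioner's tendency is the same in both settings, the expected correlation is at most √(rel(20) × rel(16)).
- At ICC 0.05: rel(20) = 1.00/1.95 = 0.513; rel(16) = 0.80/1.75 = 0.457; √(0.513 × 0.457) = 0.48.

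| ICC | rel(20) | rel(16) | Highest expected correlation |
|---|---|---|---|
| 0.01 | 0.168 | 0.139 | 0.15 |
| 0.02 | 0.290 | 0.246 | 0.27 |
| 0.03 | 0.382 | 0.331 | 0.36 |
| 0.04 | 0.455 | 0.400 | 0.43 |
| 0.05 | 0.513 | 0.457 | 0.48 |

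**2. Adding case mix.** A simulation used 90 practitioners and 2,000 runs per setting. Each practitioner has one treatment threshold, applied in both settings. The 16 profiles have fixed severities spread evenly from −1.8 to 1.8. The 20 clinic lesions have severity SD 1 within a practitioner, and the response is logistic. All severities and SDs are assumptions; the protocol gives none.

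| Threshold SD | Between-practice case-mix SD | Mean correlation, no shift | Mean correlation, shift −0.8 | Clinic rate with shift (vignette rate 50%) |
|---|---|---|---|---|
| 0.42 | 0 | 0.36 | 0.35 | 34% |
| 0.42 | 0.5 | 0.29 | 0.28 | 35% |
| 0.42 | 1.0 | 0.20 | 0.20 | 36% |
| 1.0 | 0 | 0.75 | 0.74 | 36% |
| 1.0 | 0.5 | 0.68 | 0.67 | 36% |
| 1.0 | 1.0 | 0.56 | 0.55 | 37% |

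Three effects can be told apart. Chance in counts of 16 and 20 keeps the correlation well below 1. Variation in mix between practices lowers it further. A common shift in mix moves the correlation by only about 0.01 but opens a gap of 13 to 16 percentage points between the rates.

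**3. Response described against outcome analysed.**

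| What Section 11.3 needs | Described in Sections 4, 7.1 or 7.2? |
|---|---|
| A criterion for the surgical Lens equation | Yes, if the likelihood-of-surgery rating is used as the criterion |
| Confidence in the surgical decision | No item described |
| A yes/no decision that can be counted | No item or conversion rule described |

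**The case against.** The protocol only summarises the online vignette. The instrument itself is not shown, and exact items or a cut-off could sit there or in a statistical analysis plan. Section 4 does speak of making decisions. A graded likelihood is also a natural criterion for a Lens regression, and the protocol's reference to variance accounted for fits that. All of this stands. A reader might infer that the vignette's main hypotheses cannot be tested with the data described, or that ratings will be split after the results are seen. The document supports neither inference. What remains is narrower: the confidence outcome has no described source, and the sections use different words for the response.

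On the counts, a reader might infer that the protocol will take any disagreement as evidence against the vignettes, or that the whole fidelity assessment fails. It sets no such rule: the language is exploratory, and the check on predictors works from cues recorded in both settings, so it is much less exposed to case mix. It is also fair that a low correlation would reflect chance as well as case mix, and that a uniform shift scarcely affects a correlation. These points limit the concern to the count comparison. They do not rescue it, since chance is a further reason why the counts are a poor measure of fidelity.

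**Conclusion.** The concern holds for the count-based part of the fidelity check. With the same rule in both settings, the expected correlation is at most 0.15 to 0.48 for ICCs of 0.01 to 0.05, before any difference in case mix. Under the assumed spreads, between-practice variation in mix takes it from 0.36 down to 0.20, or from 0.75 down to 0.56, and a shift in mean mix separates the rates, 50% against 34-37%. The direction of these effects is general. Their size rests on using the clinical ICC for the vignettes and on SDs that the protocol does not give.

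The mismatch between likelihood ratings and the named Lens outcomes is a separate inconsistency, clearest for confidence. Both matters concern secondary analyses; neither affects the two primary outcomes or the sample size.

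**What to change.** **Fidelity measure.** Keep the count correlation as a descriptive summary only and make the fidelity measure lesion-level:
- Fit the pre-study vignette equation as a regression on the likelihood-of-surgery rating, or as a pooled or partially pooled model with practitioner effects. Separate yes/no logistic equations per dentist should be avoided. With 16 profiles and at least five coefficients (an intercept and four cues), a consistent dentist could produce complete separation.
- Map the CRF categories to the vignette cue levels. Section 3.2.2 already lists color, luster, roughness and caries risk level among the variables assessed.
- Predict the decision on each pre-intervention lesion, and report discrimination and calibration or agreement. That phase is suitable because no study device is in use and the vignettes, as described, carry no device reading.
- Repeat the device against no-device comparison descriptively on intervention-phase lesions.

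The cost is a small amount of analysis, the mapping work, and some imprecision in practitioner-level equations. No new clinical data are needed.

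**Response wording.** Reconcile Sections 4 and 7.1 with Section 11.3. Either confirm or add a confidence item in the online vignette, or restate the Lens outcome as the likelihood rating and drop the confidence outcome. If a yes/no decision is derived from the rating, fix the cut-off before data are seen. The cost is at most one further online question per profile, or a change of text.

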12 SOURCE DOCUMENTS AND ACCESS TO SOURCE DATA/DOCUMENTS

Each participating site will maintain appropriate dental/medical and research records for this study, using the principles of good clinical practice and complying with regulatory and institutional requirements for the protection of confidentiality of subjects. Each site will permit authorized representatives of NIDCR and regulatory agencies to examine (and when required by applicable law, to copy) research records for the purposes of quality assurance reviews, audits, and evaluation of the study safety, progress and data validity.

The following clinical records will be considered source documents where they are used to complete CRFs: clinical and office charts, memoranda and recorded data from automated instruments.

The following CRFs or portions of CRFs will be considered source documents, as it is not expected that all patients' clinical charts would contain the exact information collected on these CRFs: study tooth characteristics, patient risk factors, treatment plan; questions on ethnicity, race, and highest level of education from the Patient Demographics CRF.

All study source documents must be maintained in a secure manner, and practice personnel and network personnel will have access to source documents. Study source documents may include clinical records and as such are subject to HIPAA regulations. These records will be subject to examination and copying as stated elsewhere in this section.

The CC will use a survey management system (SMS) to program the online vignette. Practitioners will be sent an email invitation with a direct link to the online vignette. After a participant submits the data it will be available in the SMS. Only study personnel i.e. the study team, National Network Director (NND) and CC staff will have access to these data elements. All research computers and associated study documents will be password-protected.

13 QUALITY CONTROL AND QUALITY ASSURANCE

For the Quality Assurance (QA)/Quality Control (QC) activities associated with data collection and processing, the CC will develop a Data Management Plan (DMP) in which the specific data QA/QC procedures will be provided and a Quality Management section in the MOP to further detail the QA/QC process. In the DMP, the procedures will include the development of automatic data quality checks in the database system and the processes related to the data manual review, discrepancy management, delinquent data handling, data updates, data verification and approval, and database audit. A work instruction will be provided to the RCs at the RAS with the specified tasks, timelines of completing the tasks, roles and responsibilities.

The MOP will detail a QA/QC process associated with data collection on pCRFs that will include quality checks at the participating practices, followed by QA/QC review at the RAS prior to and after data entry into the web system. Data entered into the system will be compared against pCRFs. The RAS staff will ensure that discrepancies generated by the system are resolved in a timely fashion based on study requirements. The RAS staff will work with practitioners to clarify any data issues and maintain a tracking log for the data changes. The Data Manager at the CC will work with the RCs to ensure that all procedures are followed and that the data are checked according to the validation requirements specified from the study protocol. At the end of the study, the RCs will ensure that all data collected by the regional offices are entered and cleaned. The Data Manager at the CC will verify the completion of data entry and clarifications by running monitoring reports. Once confirmed that the data entry are complete and the data are verified and approved for accuracy, the database will be locked for final analysis. During the study period, when interim data analysis is needed, the Data Manager will coordinate the activities with the RCs and the Statistician. The interim datasets will be provided with the data collected as of the specified date. The data in those datasets will be cleaned if possible but may contain pending issues which will be provided to the Statistician if requested. The datasets will be provided to the Statistician via secure data transfer method. The Quality Management plan is detailed in Appendix B.

For the QA/QC activities associated with vignette data collection, procedures will include the development of automatic data quality checks and the processes related to the data manual review, discrepancy management, delinquent data handling, data updates, data verification and data audits. The SPI will work closely with the CC to ensure that the electronic data are being collected appropriately and confidentially.

14 ETHICS/PROTECTION OF HUMAN SUBJECTS

14.1 Ethical Standard

The investigator will ensure that this study is conducted in full conformity with the principles set forth in The Belmont Report: Ethical Principles and Guidelines for the Protection of Human Subjects of Research, as drafted by the US National Commission for the Protection of Human Subjects of Biomedical and Behavioral Research (April 18, 1979) and codified in 45 CFR Part 46.

14.2 Institutional Review Board

It is recognized that this protocol must receive the approval of eight or more different IRBs, and each may have different criteria for subject informed consent. Therefore, different regions may have slightly varied informed consent procedures. For the purposes of this minimal risk study, any of the following will be considered acceptable by the study investigators, at the discretion of the responsible IRB: verbal consent; written consent; written information sheet provided prior to or at the time of data collection; written consent and authorization.

The protocol, consent form(s), recruitment materials and all participant materials will be submitted to the IRB for review and approval by each RAS. Approval of both the protocol and the consent form must be obtained before any participant is enrolled. Any amendment to the protocol will require review and approval by the IRB before the changes are implemented in the study.

14.3 Informed Consent Process

Informed consent is a process that is initiated prior to the individual agreeing to participate in the study and continues throughout study participation. Extensive discussion of risks and possible benefits of study participation will be provided to participants and their families, if applicable. A consent form describing in detail the study procedures and risks will be given to the participant. Consent forms will be IRB-approved, and the participant is required to read and review the document or have the document read to him or her. The investigator or designee will explain the research study to the participant and answer any questions that may arise. Participants will be given the opportunity to discuss the study with their surrogates or think about it prior to agreeing to participate. They may withdraw consent at any time throughout the course of the study. A copy of the consent document will be given to participants for their records. The rights and welfare of the participants will be protected by emphasizing to them that the quality of their clinical care will not be adversely affected if they decline to participate in this study.

Patients enrolled as participants in this study must be six years of age and older, and must be able to provide either assent or consent, following local requirements for documenting consent for research participation. Patients under the age of 19 (this age may vary by state) will need to have the consent by the parent or legal guardian and must assent to participation. By regulatory definition, children are "persons who have not attained the legal age for consent to treatments or procedures involved in the research, under the applicable law of the jurisdiction in which the research will be conducted". In the United States the legal age of adulthood is a matter of state and local law. This means that who is legally considered a child may vary from state to state; in a large majority of states 18 years of age is the legal age of adulthood, but this is not true in every state, locality, or territory. State law also may address specific circumstances in which a

person younger than the age of adulthood is legally authorized to consent to medical procedures: for example, some states allow children younger than the legal age of adulthood to consent to the provision of contraceptive services. Certain states provide a mechanism for the emancipation of minors, through which a child younger than the legal age of adulthood may gain certain civil rights, which might include the legal ability to consent to research participation.¹⁶

The consent process will be documented in the clinical or research record.

Participating practices will designate who will execute informed consent for the study. In most cases this will be the practitioner(s). Any personnel who will be assigned to obtain consent will be defined as study personnel and will complete required IRB training. Consent will be obtained in the practice prior to enrolling a subject into the study.

